6.1.1 Derived and Computed Variables

Demographics

Body Mass Index (BMI, kg/m²) will be calculated using the following formula:

$$\text{BMI} = \text{Weight (kg)} / \text{Height}^2 (\text{m}^2)$$

Immunogenicity

Values below the lower limit of quantification (recorded as “< LQ”) will be set to half that limit (LQ/2).

Values above the upper limit of quantification (recorded as “>UQ”) will be set to that upper limit (UQ).

Titer greater or equal to a given threshold is defined as binary variable for non-missing values as:

= 1, if the titer is superior or equal to the given threshold

= 0, otherwise

Seroprotection is defined as binary variable for non-missing values as:

= 1, if anti-HBs levels \geq 10mIU/mL in serum

= 0, otherwise

Seroprotection rate (SPR) is the percentage (%) of subjects achieving seroprotection.

PAREXEL International

Statistical Analysis Plan

An initial result of ≥ 5.0 and < 12.0 mIU/mL (“Indeterminate”) required duplicate retest per Laboratory Procedure Manual. In the statistical analysis, if the anti-HBs serology result is initially indeterminate, then the average of initial and repeat samples will be calculated. Seroprotection will be determined as follows: if the average of initial and repeat samples is ≥ 10 mIU/mL, then it will be considered seroprotected. If it is less than 10 mIU/mL will be considered not seroprotected.

Geometric Mean Concentration

The GMC will be calculated using the following formula:

$$10^{\left\{ \frac{\sum_{i=1}^n \log_{10}(t_i)}{n} \right\}}$$

where t_1, t_2, \dots, t_n are n observed immunogenicity titers/concentrations.

Solicited Adverse Events

Reactions at the site of injection (redness/erythema, pain, tenderness, swelling/edema, pruritus), systemic reactions (nausea/vomiting, diarrhea, headache, fatigue, myalgia) and vital signs abnormalities (fever, tachycardia, bradycardia, hypertension, hypotension, changes in respiratory rate).

Unsolicited Adverse Events

All adverse events will be characterized according to the date of occurrence related to the vaccination phase as follows:

- **Emergence before vaccination phase:** start date before the first date of injection of study vaccine.
- **Emergence during vaccination phase:** start date on or after the first date of injection of study vaccine or, adverse event increase in severity including to “serious” adverse event.

If an adverse event start date is equal to the first date of vaccination injection, missing or unknown, the adverse event will be considered as emergent.

When start and/or end dates of an adverse event are only partially known, adverse events will be categorized as emergent before, during (or after) vaccination phase using the following rules:

- If the partial end date is before ($<$) the first study vaccination (i.e., year or year & month is/are before the first study vaccination year or year & month) then the adverse event is emergent before vaccination phase.

PAREXEL International

Statistical Analysis Plan

- If the partial start date is equal or after (\geq) the first study vaccination (i.e., year or year & month is/are after or the same as the first study injection year or year & month) then the adverse event is emergent during vaccination phase.

The **maximum event severity** is the greatest severity associated with a preferred term for a reported adverse event according to the following order: Mild < Moderate < Severe < Potentially life threatening. Unknown/ Missing severity is considered as potentially life threatening.

Multiple AEs with the same PT for the same subject are counted only once.

Vaccination-related Adverse Events are those for which the cause has been evaluated by the investigator, and recorded either as very likely/certain, possibly related, probably related or unknown/missing.

Pre-study, Concomitant and Post-Study Medications

A **pre-study medication** is a medication used only before the first study vaccination (i.e. medication end date < first study vaccination date).

A **post-study medication** is a medication used only after study termination (i.e. medication start date > study termination date). This will not be collected in the clinical database and will not be reported in the CSR.

All other medications are **concomitant**.

When start and/or end dates of a medication intake are missing, the medication is considered as concomitant with the study vaccination schedule.

If the first study vaccination date is missing then the medication is considered as concomitant with the study vaccination schedule, provided that the study vaccine was administered to the subject.

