6.3.14.3 Unsolicited Adverse Events

Treatment-emergent adverse events (TEAEs) are defined as those adverse events that either start or worsen on or after the date of first vaccination.

All following TEAEs will be included in the summary tables:

- All AEs occurred on the day of vaccination (vaccination 1, vaccination 2 or vaccination 3) and during the next 27 days [date of vaccination + 27 days]
- AND
- SAEs, medically significant events (i.e., AEs medically attended) or new onset of chronic illnesses through the date of end study

If a subject missed one or two vaccination injections, the AEs for the corresponding vaccination injections will not be included in the summary. For example, one subject missed vaccination 2, the AEs for the day of vaccination 2 and during the next 27 days will be missing and not be included in the summary tables and figures.

PAREXEL International

Statistical Analysis Plan

Solicited adverse events continuing beyond Day 7 will be coded by MedDRA and combined with the respective unsolicited adverse events.

For AEs included in the summary tables defined above, numbers of AEs will be summarized by System Organ Class (SOC) and Preferred Term, and also by severity/causality to vaccine. The summaries will be presented by vaccination (any vaccination, vaccination 1, vaccination 2 and vaccination 3) and interval of onset as follow:

- Day 1 to Day 28
where the AEs will include AEs occurred on/after Day 1 (date of vaccination) until earliest date of (Day 28, date of next vaccination-1, end of study)
- Day 29 to end of considered interval
where the AEs will include SAEs, medically significant events (i.e., AEs medically attended) or new onset of chronic illnesses occurred on/after Day 29 to earliest date of (date of next vaccination-1, end of study)
- Day 1 to end of considered interval
where the AEs will include AEs occurred on/after Day 1 (date of vaccination) until earliest date of (date of next vaccination-1, end of study)

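### The SAP's missing- and partial-date rules class some adverse events that ended before any dose as emergent, and its rules for pre-study and concomitant medication conflict with no stated order of precedence

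*SAP*

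**What the plan says.** All the classification rules are in SAP section 6.1.1.

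**Adverse events.** The base definition places an event before the vaccination phase by its "start date before the first date of injection of study vaccine". The end date plays no part. Three date rules follow:

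- An event whose start date is "missing or unknown, the adverse event will be considered as emergent".
- "If the partial end date is before" the first vaccination, judged on the year or the year and month, the event is pre-vaccination.
- "If the partial start date is equal or after" the first vaccination, the event is emergent. The test is that the "year or year & month is/are after or the same as the first study injection year or year & month".

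Section 6.3.14.3 separately defines treatment-emergent events as "adverse events that either start or worsen on or after the date of first vaccination".

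**Medications.** A pre-study medication "is a medication used only before the first study vaccination", and the SAP makes this operational as an end date earlier than the first vaccination date. Everything else is concomitant, apart from post-study use. A further sentence adds: "When start and/or end dates of a medication intake are missing, the medication is considered as concomitant with the study vaccination schedule". There is no separate rule for partial medication dates.

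The SAP does not say in which order these rules apply, for adverse events or for medications.

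**The concern.** Treating an undated record as emergent or concomitant is sensible when its timing is unknown. It is not sensible when the end date already shows that the event or the medication was over before the first dose. Such an event neither began nor worsened after vaccination, so it cannot meet the section 6.3.14.3 definition, whatever its start date.

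The SAP accepts this logic in its partial-end-date rule, which takes an earlier end date as proof of pre-vaccination status. But that rule is worded only for the less precise kind of end date. Taken literally, recording the end date in full removes the one rule that would classify the event correctly.

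Two things are at stake. Some records that cannot be related in time to vaccination may enter the treatment-emergent and concomitant-medication tables. And two programmers could follow the SAP faithfully and produce different tables from the same data.

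**Working it through.** The SAP states no figure on this point, so there is none to reproduce. The check applies the section 6.1.1 rules literally to test records. The first vaccination date, 20 June 2018, is assumed only to exercise the rules. Every test record ended before it: 5 June is 15 days earlier (20 − 5), and 10 May is 41 days earlier (21 days left in May + 20).

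**Adverse events**

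| Case | Start date | End date | Rule(s) that apply | Result |
|---|---|---|---|---|
| 1 | missing | 5 Jun 2018 | missing start | emergent |
| 2 | missing | 10 May 2018 | missing start | emergent |
| 3 | Jun 2018 | 5 Jun 2018 | partial start | emergent |
| 4 | 2018 | 10 May 2018 | partial start | emergent |
| 5 | missing | May 2018 | missing start; partial end | emergent and before |
| 6 | 2018 | May 2018 | partial start; partial end | emergent and before |

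In cases 1 to 4 the end date is complete. Only a start-date rule applies, nothing in section 6.1.1 points the other way, and the result contradicts section 6.3.14.3. In cases 5 and 6 the end date is partial. Two rules apply with opposite answers, and nothing says which prevails.

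Cases 4 and 6 differ only in whether the day of the end date is known. With the day unknown, one rule gives the correct class. With the day known, no rule does.

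**Medications**

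| Case | Start date | End date | Rule(s) that apply | Result |
|---|---|---|---|---|
| 7 | missing | 5 Jun or 10 May 2018 | pre-study definition; missing-date rule | pre-study and concomitant |
| 8 | Jun 2018 | 5 Jun 2018 | pre-study definition | pre-study |

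Case 7 is the conflict. The end date satisfies the pre-study definition, and the missing start date triggers the concomitant rule. Case 8 has no conflict if a partial start date is not read as missing, so for medications the problem lies in the missing-date sentence alone.

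**After the fix.** If an end date before the first vaccination is applied first, cases 1 to 6 are all pre-vaccination and cases 7 and 8 are pre-study. For cases 5 and 6, May 2018 is an earlier month than June 2018. No record keeps two classes.

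**Where the records would go.** Section 6.3.11 tabulates concomitant medication on the Safety Set. Section 6.3.14.3 tabulates treatment-emergent events, and also plans a listing of pre-vaccination events, so the SAP expects some to exist. The schedule in section 6.1 collects medications from screening, up to 28 days before Day 0. Routine collection of unsolicited non-serious events starts at Visit 1. Only serious events, medically significant events and new chronic illnesses are collected continuously.

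**The case against.** The strongest reply has four parts.

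**The rules can be read in order.** On that reading the pre-study definition comes first, and the missing-date sentence governs only records not already classified. The partial-end rule compares year and month, and a complete date also contains these, so a programmer might extend it to a complete end date in an earlier month. Part of this stands. A reader might infer that the rules clearly override a known end date throughout. The text does not support that for medications or for partial end dates, where it shows an unresolved conflict. But no order is written down. Even the generous reading of the partial-end rule leaves an end date in the vaccination month unprotected (cases 1 and 3), and leaves the missing-start rule in conflict with it (case 2).

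**Few adverse events can be affected.** Collection of routine non-serious events starts on the day of the first vaccination. An event that ended earlier would normally be recorded only if serious, medically significant or a new chronic illness, and a missing start date is less likely for those. This stands, and it limits the size of the adverse-event part.

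**Section 6.3.14.3 limits the effect.** Its definition would exclude these events, and its by-vaccination tables use intervals of onset, into which an event without a start date does not fit. This stands only in part. It shows that the two sections disagree, and the SAP does not say which one governs the programming.

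**Over-counting is conservative and equal across arms.** This is true, and the outputs are descriptive. But a worst-case rule is meant for uncertain timing, and here the end date removes the uncertainty.

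**Conclusion.** The point holds as an error of specification with small consequences. For adverse events with a complete end date before the first vaccination, the literal rules give a class that contradicts section 6.3.14.3. For adverse events with a partial end date, and for medications with a missing start date, the rules give two answers and no precedence.

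The SAP gives no count of affected records and no rate of missing start dates. A reader might apply an assumed rate to the 2838 randomized subjects to obtain a number of false concomitant medications. The document supports neither that rate nor that denominator, since section 6.3.11 uses the Safety Set. No count is offered here.

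A reader might also infer bias in the vaccine comparison or in the immunogenicity results. That does not follow. The rules are the same in all arms. Section 6.3.14 describes the affected outputs without a hypothesis test. Per-protocol exclusion for prohibited medication goes through the deviation review before unblinding (sections 6.2.5 and 6.3.7), and no link from this derivation to that review is stated.

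The conclusion assumes that the rules are programmed as written and that at least some records have an end date before the first dose with a missing or partial start date.

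**What to change.** Add one step to section 6.1.1, ahead of all other date rules: where the end date is complete and earlier than the first vaccination, or partial with a year (or year and month) earlier than that of the first vaccination, class the adverse event as pre-vaccination and the medication as pre-study, whatever the start date shows.

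Then state that the missing-start, partial-start and missing-medication-date rules apply only to the records that remain. The conservative default is kept wherever the end date does not settle the matter, for example when it is missing or is partial and falls in the vaccination month.

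The cost is about two sentences in the SAP and a minor change to two derivations. No data collection, analysis set or hypothesis test changes.

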6.2 Analysis Sets

6.2.1 All Enrolled Set

The All Enrolled Set will be defined as all screened subjects who provide informed consent and provide demographic and/or baseline screening assessments, regardless of the subject's randomization and treatment status in the study.

6.2.2 Safety Set

All subjects in the All Enrolled Set who receive a study vaccination. Subjects will be analyzed as vaccinated, i.e., a subject will be assigned according to the vaccination received.

PAREXEL International

Statistical Analysis Plan

In case of vaccination error, subjects will be analyzed as initially “treated” (i.e., according to the first vaccine a subject receives, rather than the vaccine to which the subject is randomized).

6.2.3 Intent-to-Treat (ITT)

All subjects in the All Enrolled Set who were randomized.

In case of vaccination error, subjects in the ITT will be analyzed “as randomized” (i.e., according to the vaccine a subject was designated to receive, which may be different from the vaccine the subject actually received). Any subject who received the wrong vaccination will not be excluded from the ITT.

6.2.4 Full Analysis Set (FAS)

All subjects in the All Enrolled Set who receive at least one vaccination and provide at least one evaluable serum immunogenicity sample both at baseline and after baseline.

In case of vaccination error, subjects in the FAS will be analyzed “as randomized” (i.e., according to the vaccine a subject was designated to receive, which may be different from the vaccine the subject actually received). Any subject who received the wrong vaccination will not be excluded from the FAS.

If a subject is unblinded during the study, he/she will be included in the FAS.

6.2.5 Per Protocol Sets

6.2.5.1 Per Protocol Set 1 (PPS1)

All subjects in the FAS who:

- received all 3 vaccinations
- have an evaluable serum immunogenicity samples at baseline and at the time point of interest
- are seronegative at baseline
- had no major protocol deviations leading to exclusion, which will be identified prior to unblinding.

A major protocol deviation for the purpose of exclusion from the PPS1 is defined as a protocol deviation that is considered to have a significant impact on the immunogenicity result of the subject.

These will be identified prior to unblinding and analysis and may include:

- subjects enrolled who did not meet study entry criteria
- subjects who did not receive the correct treatment
- subjects who developed withdrawal criteria but were not withdrawn
- subjects who received a prohibited concomitant medication

PAREXEL International Statistical Analysis Plan

- subjects with a deviation identified through monitoring visits or otherwise, where the deviation is judged to impact the reliability of subject immunogenicity results

PPS1 will be used for the primary endpoint analysis.

6.2.5.2 Per Protocol Set 2 (PPS2)

All subjects in PPS1, but excluding those who attended study visits outside of the following windows:

- V3/Day 168 (+/- 28 days)
- V4/Day 196 (-7/+14 days)

PPS2 will be used for the primary, secondary, and exploratory endpoints.

In case of vaccination error, subjects in PPS1 and/or PPS2 will be analyzed “as randomized” and the subject who received the wrong vaccination will be excluded from PPS1 and/or PPS2. If a subject receives a vaccine from the wrong kit number, but the same as the one the subject was randomized to, the subject will not be removed from PPS1 and/or PPS2.

If a subject is unblinded during the study, except for suspected unexpected serious adverse reaction (SUSAR), he/she may be excluded from PPS1 and/or PPS2 based on sponsor’s decision with respect to any potential bias that may be introduced in the analysis of the primary and key secondary immunogenicity analyses.

6.2.6 Sub-study Analysis Set (SSA)

All subjects in the All Enrolled Set who actually receive at least one dose of study vaccination and participated in the clinical laboratory sub-study.

6.2.7 Sub Groups

The following key sub-groups of interest will be pre-specified:

- Gender (male vs female)
- BMI (≤ 30 vs > 30)
- Smoking Status (current vs past or non-smoker)
- Daily alcohol consumption (≥ 4 drinks/day vs 2-3 drinks/day vs 0-1 drink/day)
- Non-study licensed vaccine (no vaccination vs vaccination)
- Race (White vs Black or African American vs Other)
- Ethnicity (Hispanic or Latino vs Non Hispanic or Latino)
- Country/region (United States vs Canada vs Europe)

PAREXEL International
Statistical Analysis Plan

6.3 Statistical Analysis Methods

6.3.1 Listings and Descriptive Statistics

All original and derived parameters as well as population characteristics will be listed and described using summary statistics. Frequency counts (number of subjects [n] and percentages) will be made for each qualitative variable. Descriptive statistics (n, mean, standard deviation [SD], median, minimum and maximum) will be calculated for each quantitative variable (unless otherwise stated). All listings will include repeated and unscheduled measurements.

All descriptive statistics will be presented by lot and treatment and visit. The baseline for all measurements (where applicable) will be the last pre-vaccination measurement. Descriptive statistics for all data obtained at Screening and follow-up will be presented separately.

6.3.2 Statistical Significance Level

All statistical tests will be two-sided and will be performed at the 5% level of significance, unless otherwise stated.

6.3.3 Software

All statistical analyses will be performed using Statistical Analysis Software (SAS®) Version 9.3 or later.

6.3.4 Study Visits

For laboratory data, vital sign data and physical examination data, data will be summarized or listed using the scheduled visits (See [Table 1](#)).

Table 1: Study Visits and Analysis Visits

Nominal Study Visit	Analysis Visit	Target Study Day*
Screening	Screening	-28
Visit 1	Day 0	1
Visit A1	Day 7	8
Visit 2	Day 28	29
Visit A2	Day 35	36
Visit 3	Day 168	169
Visit A3	Day 175	176
Visit 4	Day 196	197
Visit 5	Day 336	337
Unscheduled	Unscheduled	

* Study Day 1 is the date of first vaccination is administered to the subject. Study Day = (date of event/visit – first vaccination date) if it is before the first vaccination. Study Day = (date of event/visit – first vaccination date) + 1 if it is on or after the first vaccination.

PAREXEL International

Statistical Analysis Plan

Unscheduled assessments will be included in listings, but not in summaries. If a subject has multiple assessments within the same post-baseline analysis visit, the following rules will be established to select the data to be included in the descriptive summary:

- If multiple assessments occur within a given analysis visit, the assessment closest to the target study day will be used for analysis purposes.
- If there are 2 or more values equal distance to the target study day, then the last assessment, within the analysis visit, will be used in the analysis.

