	
(a) Or earlier in case of withdrawal (reason for withdrawal to be documented in eCRF)
 
(b) Full physicals to be done at screening or pre-vaccination at Day 0. History-directed physicals can be completed at subsequent visits.
 
(c) Blood sample will be taken before vaccination
 
(d) Vital signs will be recorded before and 30 minutes after each vaccination.
 
(e) Subjects will be instructed to record solicited and unsolicited AEs. There will be a telephone call 7 days (+/-2 days) after each vaccination, and 28 days (+/- 7 days) after the second vaccination to inquire about AEs. If there is a reaction the subject may be asked to come for a supplemental visit (not represented in this table) to assess severity at the discretion of the investigator. Follow-up until resolution.
 
(f) Only AEs requiring medical attention
 
(g) All AEs
 
(h) NOCI = new onset of chronic illness
 
(i) Visit 4 should be scheduled at least 3 weeks after Visit 3
 
(j) Blood sample collected 7 days (-3/+7 days) after vaccination
 
*Additional visits (A1, A2 and A3) required for study subjects at select sites participating in the clinical laboratory sub-study.
									

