6.3.14.4 Clinical Safety Laboratory Tests (Hematology, Biochemistry and Urinalysis)

Laboratory values (hematology, biochemistry and urinalysis) will be listed by subject and study time point including changes from baseline (with the exception of urinalysis). The baseline for the laboratory values will be the latest non-missing result obtained before first vaccine injection.

All laboratory (e.g., hematology, biochemistry) data will be summarized using descriptive statistics. Summaries will be provided for the observed values and changes from baseline at each scheduled visit. The changes in biochemistry and hematology from baseline will only be calculated in the clinical laboratory sub-study analysis set (SSA). In addition, absolute and change from baseline values will be categorized according to the toxicity scales (See protocol Appendix 3 for laboratory parameters) and summarized by time point using shift tables.

PAREXEL International
Statistical Analysis Plan

6.3.14.5 *Vital Signs*

Vital signs data will be listed by subject including changes from baseline. The baseline for the vital signs measurements will be the latest non-missing results obtained before first vaccine injection.

All vital sign data will be summarized using descriptive statistics. Summaries will be provided for the observed values and changes from baseline at each scheduled visit. In addition, absolute and change from baseline values will be categorized according to the toxicity scales (see protocol Appendix 3 for vital signs) and summarized by time point using shift tables.

6.3.14.6 *Physical Examination*

The results of the physical examination will be listed by subject and time-point. Any clinically significant difference in physical examination from previous visit will be summarized by visit.

PAREXEL International
Statistical Analysis Plan

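### Laboratory and vital-sign toxicity grades are tabulated only by scheduled visit, so a worst grade seen outside those visits, or displaced within one, reaches listings only

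*SAP*

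**What the plan says.** SAP 6.3.4 sets the rule for three data types: "For laboratory data, vital sign data and physical examination data, data will be summarized or listed using the scheduled visits". It then says: "Unscheduled assessments will be included in listings, but not in summaries". For several results in one post-baseline analysis visit it adds: "If multiple assessments occur within a given analysis visit, the assessment closest to the target study day will be used for analysis purposes". If two results are equally distant, the last is taken.

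SAP 6.3.14.4 applies this to laboratory data: "Summaries will be provided for the observed values and changes from baseline at each scheduled visit". On grading it says that "absolute and change from baseline values will be categorized according to the toxicity scales", and that these are "summarized by time point using shift tables". SAP 6.3.14.5 gives the same arrangement for vital signs.

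For reactions, footnote (e) to the schedule in SAP 6.1 allows extra attendance, as follows: "the subject may be asked to come for a supplemental visit (not represented in this table) to assess severity at the discretion of the investigator".

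SAP 6.3.1 keeps repeat and unscheduled measurements in all listings.

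**The concern.** A by-visit rule suits tables of means and mean changes, where each subject should contribute one comparable value per visit. Toxicity grading asks something else: how many subjects reached a given grade at any time after vaccination. For that question, a rule that drops unscheduled results and ignores grade when choosing among several can only leave the answer unchanged or lower it.

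The SAP follows the worst-case principle elsewhere. Under 6.3.14.3 a recurring adverse event is counted at its maximal severity, and under 6.1.1 a missing severity is treated as the highest category. Graded laboratory and vital-sign measurements have no corresponding maximum-grade summary. At stake is the completeness of the descriptive safety tables, not the primary or secondary immunogenicity conclusions.

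**Working it through.** No power, rate or margin is involved and the plan states no figure to reproduce, so the check is to follow a result through the rules.

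**1. What is scheduled after each dose.**
- Sub-study chemistry and haematology (SAP 6.1, footnote (j)): one draw after each vaccination, at A1, A2 and A3. The target is 7 days with a window of -3/+7, so from 7 - 3 = 4 to 7 + 7 = 14 days after the dose.
- Vital signs (SAP 6.1, footnote (d)): before and 30 minutes after each vaccination, and again at Visit 4.

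**2. How an extra result is assigned.** Table 1 in 6.3.4 maps nominal visits to analysis visits and has its own row for unscheduled results. It gives no date windows. Two readings are possible, and the outcome depends on which applies. Days below are counted from the vaccination.

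| Laboratory results in one subject | Extra result keeps its unscheduled label | Both results assigned to A1 by date |
|---|---|---|
| A1 draw on day 7 normal; extra draw on day 12 Grade 3 | Day 12 is unscheduled and is only listed | Distances 0 and 5 days; day 7 is used, day 12 is only listed |
| A1 draw on day 4 Grade 3; repeat on day 7 normal | Repeat is unscheduled; the Grade 3 value is tabulated | Distances 3 and 0 days; day 7 is used, Grade 3 is only listed |

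The first pattern loses the higher grade under either reading. The second loses it only under date assignment. Two results assigned to one visit on the same day are tied, so the later is kept. If an abnormal value is repeated that day and has recovered, the recovered value is the one tabulated.

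**3. Whether another table catches it.**
- The solicited-event tables (6.3.14.2) cover local and systemic reactions, fever, and heart rate, blood pressure and respiratory rate for 0-30 minutes. They do not cover laboratory values.
- The unsolicited-event tables (6.3.14.3) catch a laboratory abnormality only if it is reported as an adverse event.
- The by-visit shift tables do not give a subject-level maximum even from scheduled results. A subject with Grade 2 at A1 and Grade 3 at A3 appears once in each table, and no planned table counts that subject once at Grade 3.

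**4. Size.** Let p be the proportion of subjects whose worst post-vaccination grade is at or above some level. Let q be the share of these in whom that level is seen only on results that the rules leave out. The by-visit tables can then reveal at most p x (1 - q). The SAP gives neither p nor q, nor the size of the sub-study. Since q may be zero, the direction of the effect is known but its amount is not.

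**The case against.** The strongest case against the point runs as follows. The rule is clear and not contradicted elsewhere. Restricting by-visit tables to scheduled results avoids uneven ascertainment from discretionary testing. No test or decision depends on these tables, and every excluded value is listed. Supplemental visits are held to assess the severity of a reaction, and that severity is not lost: the unscheduled rule does not extend to adverse events, which are summarised by severity.

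Most of this stands, and it limits what can be claimed.
- A reader might infer that the worst values are often found at extra visits. Footnote (e) does not support that. It says only that a subject may be asked to attend, names no tests, and gives no frequency.
- A reader might infer that the worst values never reach the shift tables. They do when they occur at a scheduled visit and are the result selected.
- A reader might infer that vital-sign grades are summarised only by scheduled visit. Fever and the 0-30 minute abnormalities are also graded as solicited adverse events, overall and after each vaccination. Fever is not confined to the first 30 minutes.
- A reader might infer that the loss is greater in a more reactogenic arm. Nothing in the SAP shows that.

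What the objection does not answer is the laboratory gap. Uneven ascertainment is a reason to keep the by-visit tables as they are. It is not a reason to have no worst-grade table beside them.

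**Conclusion.** The point holds in a limited form. Under 6.3.4, 6.3.14.4 and 6.3.14.5, a worst post-vaccination grade seen only at an unscheduled assessment, or displaced by the selection rule, enters no planned laboratory or vital-sign summary. The shift tables can therefore understate the worst grade. The main exposure is the sub-study laboratory data; vital signs are partly covered by the solicited-event tables.

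The conclusion assumes that some laboratory or vital-sign results are taken outside the schedule or repeated within a visit. The SAP provides for handling such results but does not say how many to expect. Neither the amount of understatement nor any imbalance between arms can be estimated from it. No data are lost, and the immunogenicity conclusions are unaffected. This is an inexpensive improvement to safety reporting.

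**What to change.** - Keep the 6.3.4 rules for descriptive statistics and by-visit shift tables.
- Add to 6.3.14.4 (on the sub-study analysis set) and to 6.3.14.5 one shift table each, from baseline to the worst post-vaccination toxicity grade, overall and after each dose. Use all scheduled, repeat and unscheduled post-vaccination results.
- State in 6.3.4 that its exclusion and selection rules do not apply to these worst-grade tables. They then do not depend on how an extra result is assigned to a visit.
- Define the period for each dose. It could run from that vaccination to the next, or to the end of study after the last. A pre-dose vital-sign reading on the day of a later vaccination would then count towards the preceding dose.

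The cost is SAP wording and a few tables from data already collected and listed. The drawback is that subjects with more measurements have more chance of showing a high grade. A footnote should say so.
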